5.3 Expected duration of trial

As stated above and illustrated in 3.5 and 3.6, the trial will end after the follow-up visit at week 16 with a window of 2 weeks before and after that timing, or if the participant requests to exit the study. The inclusion period will be covering Q3 and Q4 of 2022 (06/2022 – 12/2022) with last possible visit performed in Q1 of 2023 (end of 03/2023). Since this study does not involve an IMP, we do not expect any study-related adverse events to occur that might necessitate premature termination of the study.

6. Trial Procedures

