4.2 Primary endpoints

Difference in mean change of total ASES (Arthritis Self-Efficacy Scale) score from baseline to week 16 ± 2w in the intervention group when compared to the control group. The ASES is a patient-reported questionnaire consisting of 20 items to measure one's arthritis-specific self-efficacy across 2 subscales: self-efficacy for managing pain (PSE, range 5-50), and self-efficacy for controlling other symptoms (OSE, range 6-60). Both scores can be summed to derive a total ASES-score (range 11-110).

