In addition to usual care, participants in the intervention group will receive unrestricted, free-of-charge and unincentivized access to the Sidekick Health application. The application was designed by the company Sidekick Health (Iceland) with the support of pharmaceutical company Pfizer for the adaptation of the app to the Belgian public, with a design centered particularly around promoting behavioral change and a strong focus on gamification techniques. It includes an educational module (Appendix A) that was specifically developed for patients with RA in collaboration with 10 rheumatologists. In addition, the app allows users to record nutritional diaries, subjective sleep quality and physical activity (manually or through wearable activity trackers or the smartphone's accelerometer), while also providing several physical and mindfulness-based exercises and the option to record PROs such as the RAID questionnaire. Reminders or alerts can be set up and customized by the users in the app itself, according to their personal preferences. These logs are stored in the application's designated data cloud, from which all identifiable data will be removed upon termination of the account at the end of the study (also see section on Data handling). The educational program on the app runs for a period of 16 weeks.

In all groups, an in-person visit will be scheduled at baseline and after 16 weeks, with a window of 2 weeks before and 2 weeks after this time point, taking place at the Rheumatology outpatient clinic of the participating centers. At the baseline and week $16 \pm 2w$ visits and in all groups, we will collect routine clinical data, including clinical examination and readily available blood samples, DAS28-CRP/SDAI, and HAQ, as well as trial questionnaires in the form of the ASES, PCS, IPAQ-S, and PSQI (see 3.5 and 3.6). The following data will only be collected at baseline, also in all groups: RA phenotype (RF/ACPA/erosive), disease duration, past and current DMARD-therapy, comorbidities if present, educational level, and participants' demographic characteristics.

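### The latest visit date in section 5.3 leaves anyone enrolled after 23 December 2022 without an in-window primary-endpoint visit

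*Combined protocol and SAP*

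**What the plan says.** Section 5.3 (Expected duration of trial) fixes three things. Recruitment: "The inclusion period will be covering Q3 and Q4 of 2022 (06/2022 – 12/2022"). Follow-up: "the trial will end after the follow-up visit at week 16 with a window of 2 weeks before and after that timing". Calendar end: "with last possible visit performed in Q1 of 2023 (end of 03/2023").

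The visit window is the same elsewhere. Section 4.4 states that "an in-person visit will be scheduled at baseline and after 16 weeks, with a window of 2 weeks before and 2 weeks after" the 16-week point. Section 4.2 defines the primary endpoint as "Difference in mean change of total ASES (Arthritis Self-Efficacy Scale) score from baseline to week 16 ± 2w", so any visit from week 14 to week 18 supplies valid primary-endpoint data. Section 4.4 also notes: "The educational program on the app runs for a period of 16 weeks".

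**The concern.** The closing date of inclusion, the visit window and the latest visit date are linked: once two are fixed, the third follows. Here the interval from the end of December to the end of March looks shorter than the follow-up that every participant needs.

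If the end date were applied as written, the last patients enrolled would have no valid week 16 assessment of the primary endpoint, or of the secondary pain catastrophizing endpoint, which has the same timing. That loss would come from the calendar rather than from patients leaving, so it would add to the 10% dropout allowed for in section 9.1. Patients enrolled slightly earlier could be seen in window, but only at its early side, before the 16-week app program had ended.

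**Working it through.** **Inputs**

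- Inclusion period: 06/2022 to 12/2022 (section 5.3), read as 1 June to 31 December, 214 days. The same sentence calls this Q3 and Q4, which taken literally is 1 July to 31 December, 184 days.
- Latest visit: end of 03/2023 (section 5.3), read as 31 March 2023.
- Visit window: weeks 14 to 18 (sections 4.2, 4.4 and 5.3).
- Total N = 120, dropout 10%, non-parametric allowance 15%, effect size 5.5/9.4 = 0.585 (section 9.1).
- Even accrual is an assumption. The documents give no accrual curve.

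**Step 1: can the stated end date be reproduced?**

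31 December 2022 to 31 March 2023 = 31 + 28 + 31 = 90 days = 90/7 = 12.9 weeks. The earliest allowed visit is at 14 × 7 = 98 days. The stated date is 8 days short of that and cannot be reproduced from an inclusion period that runs to the end of December.

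Counting forward from 31 December 2022:

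| Visit | Date |
|---|---|
| Week 14 | 8 April 2023 |
| Week 16 | 22 April 2023 |
| Week 18 | 6 May 2023 |

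**Step 2: who is affected?**

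Latest workable baseline = 31 March 2023 minus the follow-up time.

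| Requirement | Latest baseline |
|---|---|
| Week 14 reachable | 23 December 2022 |
| Week 16 reachable | 9 December 2022 |

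- Baseline 24 to 31 December (8 days): no in-window visit is possible.
- Baseline 10 to 23 December (14 days): a visit is possible from week 14 to just under week 16. It is valid under section 4.2 but falls before the app program ends.

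**Step 3: how many?**

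Share = affected days / days of inclusion; patients = share × 120.

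- No valid visit, start 1 June: 8/214 = 3.7%; × 120 = 4.5 patients.
- No valid visit, start 1 July: 8/184 = 4.3%; × 120 = 5.2 patients.
- In window but only before week 16, start 1 June: 14/214 = 6.5%; × 120 = 7.9 patients.

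Range for the first group: close to 0 if hardly anyone is enrolled in the last week of December. If enrolment began only on 3 November 2022, the date of version 6.3 (an assumption), there are 59 days of inclusion, and 8/59 = 13.6%, or about 16 patients.

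**Step 4: what would it do to power?**

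The plan's N reproduces: a two-sample t-test with d = 0.585, two-sided 0.05 and 80% power needs 46.8 per group, 94 in total; 94 × 1.10 × 1.15 = 118.9, so 119, in line with the stated 120.

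Evaluable per group = 60 × 0.90 × (1 − calendar loss). For the non-parametric column this is divided by 1.15.

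| Calendar loss | Evaluable per group | Power, t-test | Power, 15% penalty |
|---|---|---|---|
| None | 54.0 | 85.4% | 80.1% |
| 3.7% | 52.0 | 84.0% | 78.6% |
| 13.6% | 46.7 | 79.8% | 74.0% |

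**The case against.** Three points can be made in defence of the plan.

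First, section 5.3 describes an expected duration, and no analysis rule discards a visit by calendar date. Section 5.2 excludes participants for absent questionnaire data or for not using the app, and section 9.2 has no date cut-off. A visit in April 2023 that falls in weeks 14 to 18 meets the endpoint definition and would be analysed. This stands, and it is why the severity is minor. It does not remove the conflict, because the sentence words the date as a limit. If later visits are intended, the sentence should say so.

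Second, the dates are given by month. If the last December inclusion fell on or before the 23rd, everyone could be seen in window. That is true, but nothing in the documents says that inclusion stops before the month ends.

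Third, the effect on power is small, and section 9.2 plans multiple imputation for data missing at random. This also stands. Under even accrual the loss costs about 1.5 percentage points, although with the non-parametric penalty the plan starts at 80.1% and has no slack.

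A stronger reading is tempting. Everyone enrolled after 9 December misses the nominal week 16 date, which is 22/214 = 10.3% or about 12 patients, so a reader might infer that the calendar costs about 10% of the primary-endpoint data and uses up the whole dropout allowance. The documents do not support this. Section 4.2 accepts visits from week 14, so 14 of those 22 days still yield valid data. Likewise, patients enrolled after 25 November (36/214 = 16.8%) lack the full window by 31 March, but most of them simply have fewer days in which to be scheduled. That is not a loss of data.

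**Conclusion.** Section 5.3 is wrong as written, with minor severity. The conflict itself follows from the calendar and needs only one reading, that inclusion through 12/2022 runs to 31 December.

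Its size is less certain. About 4% of patients would have no in-window visit if accrual is even, with a plausible range from near 0 to about 14% depending on when enrolment started and how much of it falls in late December. The roughly 6.5% who could be assessed only before week 16 are a matter of timing within the window, not missing data. Any loss at all depends on sites enforcing the end date.

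**What to change.** In section 5.3, change the latest visit date from the end of March 2023 to 6 May 2023, which is 31 December 2022 plus 18 weeks. Leave the inclusion period and the week 16 ± 2 window unchanged, so that every participant has the full window and the endpoint definition is untouched.

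The change is one sentence. It costs 36 days, about five weeks, of additional follow-up. Ending inclusion early instead is not needed and would give up recruitment time.

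The same sentence can be tidied by making its quarter labels agree with its months: June 2022 lies in Q2, not Q3, and the new visit date falls in Q2 of 2023.

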6.1 By visit

Visit 1 (screening and baseline):

- Recruitment of eligible participants after informed consent at the Rheumatology outpatient clinic of the participating centers.
- Two-step randomization, as described above, into a control group and an intervention group (1:1), which will in turn be re-randomized in a 1:1 ratio into a weekly RAID arm and a monthly RAID arm.
- Downloading Sidekick Health app (intervention group only).
- Collection of demographic and disease-related characteristics for included patients: age, sex, RF and ACPA status, radiographic erosions, disease duration, current DMARD-therapy, prior DMARD-therapy, BMI, smoking status, education level.
- Collection of relevant medical and surgical history and comorbidities.
- Physical examination, including TJC28 and SJC28, measurement of weight and height.
- Patient's and Physician's global assessment (VAS).

- Participants in both the control and intervention groups will be asked to complete the following questionnaires considering self-efficacy (ASES), patient-reported outcomes (RAID), daily functioning (HAQ), pain catastrophizing (PCS), physical activity (IPAQ-S) and sleep quality (PSQI). Questionnaires will be completed in MyNexuzHealth (an online patient communication platform used by the University Hospitals Leuven Belgium) or, if not possible, in a pen-and-paper form at the outpatient clinic.

- Self-efficacy: The ASES is a patient-reported questionnaire (25) consisting of 20 items to measure one's arthritis-specific self-efficacy across 2 subscales: self-efficacy for managing pain (PSE, range 5-50), and self-efficacy for controlling other symptoms (OSE, range 6-60). Both scores can be summed to derive a total ASES-score (range 11-110).
- Patient-reported outcomes: The RAID questionnaire is a patient-derived differentially weighted 7-item tool assessing pain, functional disability, fatigue, sleep, coping, physical and emotional well-being.
- Daily functioning: The HAQ is a self-administered questionnaire, that assesses the ability in performing daily life activities and measures the functional impact of rheumatoid arthritis (26). The HAQ is routinely collected at the rheumatology outpatient clinic at University Hospitals Leuven.
- Pain catastrophizing: The PCS is a patient-reported questionnaire with 13 items scored on a 0-4 Likert scale, resulting in a total score of 0-52 with subscores for rumination, magnification, and helplessness (27). Higher scores indicate more catastrophic perceptions concerning pain.
- Physical activity: The IPAQ short form is a 7-item questionnaire enquiring about physical activities during the last 7 days (28). A specific activity score is obtained for different domains, each being multiplied with the accompanying mean metabolic equivalent (MET) value. This leads to a total score corresponding with low, moderate or high physical activity.
- Sleep quality: The PSQI is a patient-reported questionnaire developed to measure sleep quality through 19 items across 7 domains (29). The resulting total score ranges from 0-21, with scores of 5 or higher being defined as poor sleep quality.

- Disease activity will be monitored in both participant groups with the DAS28-CRP and SDAI scores, using internationally validated cut-offs. DAS28-CRP is a composite score that combines a patient's global assessment of disease activity, a clinical examination with counts of painful and swollen joints, and CRP as an inflammatory laboratory parameter (30). SDAI is an analogous composite score that additionally includes the physician's/evaluator's global assessment of disease activity and has its own validated cut-offs (31). These examinations are part of routine care.

- Results of both clinical data and the obtained questionnaires will be extracted from the electronic medical patient file used in UZ Leuven and other participating centers (KWS) or, if not possible, from the completed pen-and-paper forms.

Intervention phase (between baseline and week 16 ± 2w visit)

While using the SideKick Health app, patients in the intervention group will have the opportunity to actively log data relating to their diet, physical activity, sleep quality, stress (such as minutes spent completing relaxation exercises in the application), vital signs, and fill out short questionnaires, for example the RAID questionnaire, integrated in the application. Among these, only completion of the RAID questionnaire is actively stimulated and expected as part of the study, all other functions can be used on a voluntary basis.

As stated before, one arm of the intervention group will be asked to complete the RAID questionnaire on a weekly basis, the other one will do this on a monthly basis. During this phase of the study user behavior statistics will also be collected as described above (number of times the app was used, how often certain questions were answered, ...).

Visit 2 (week 16 ± 2)

- Participants in both the control and intervention groups will be asked to again complete the previously outlined questionnaires considering self-efficacy (ASES), patient-reported outcomes (RAID), physical disability (HAQ), pain catastrophizing (PCS), physical activity (IPAQ-S), and sleep quality (PSQI). Questionnaires will be completed in MyNexuzHealth or in pen-and-paper form at the outpatient clinic if not available. In addition, disease activity will again be assessed as part of routine care by way of the DAS28-CRP and SDAI scores.
- The study will end after this visit. The participants will be free to continue with the Sidekick-application at their leisure, or alternatively, to terminate the account. Upon termination of the account, all stored personal data will be removed from the application's data cloud (also see section on Data handling).

6.2 Laboratory tests

Laboratory tests obtained for this study will be limited to those collected as part of routine care in hospital or by the patient's general practitioner, for instance the collection of CRP to calculate DAS28-CRP and SDAI scores. No additional laboratory tests will be conducted for the purposes of this study.

6.3 Other investigations

Other than any investigations required as part of routine care, no additional investigations will be carried out for this study.

7. Assessment of efficacy

Efficacy of this app-based educational, monitoring, and lifestyle intervention will be studied by assessing changes in self-efficacy (ASES), physical activity (IPAQ-S) and sleep quality (PSQI), while the intervention's effect on pain catastrophizing will be studied in a non-inferiority setting to exclude any

(negative) effects of systematic PRO-registration on pain perceptions. As stated in the sections on Trial Objectives and Design, the primary endpoint will be the difference in mean change of total ASES-score from baseline to week 16 ± 2 w in the intervention group when compared to the control group, while the intervention's effect on pain catastrophizing was chosen as a secondary endpoint. Sample size calculations were based on obtaining 80% power for both the primary and the secondary endpoint, as outlined in section 9.

In addition to the information obtained from the questionnaires, we will also study participants' continued engagement with the app and its possible effects on intervention efficacy as an exploratory endpoint, as described above.

8. Assessment of Safety

8.1 Specification, timing and recording of safety parameters

Clinical examination will be conducted as prescribed in the normal procedures of standard of care. Results of blood samples to calculate the DAS28-CRP and SDAI scores, will only be used if already available, no extra blood samples will be taken for the study.

8.2 Procedures for recording and reporting adverse events (AE)

Since the study intervention does not include an IMP, recording and reporting of adverse events is not applicable for this study.

8.3 Treatment stopping rules

Not applicable for this study.

9. Statistics

9.1 Sample size

For the primary outcome, we opted for a superiority design aiming to reject the null hypothesis that there would be no difference between the intervention and control groups in the change of the total ASES-score from baseline to week 16. Sample size calculation was based on the previously proposed minimal clinically important difference in the ASES-score, corresponding with a change of 5.5 on either the pain or other symptoms subscale (13,25). Moreover, in a recently published, large prospective study from our research group, including 379 patients with RA, the mean (\pm SD) self-efficacy for pain (PSE) was 31.8 (\pm 8.9) and self-efficacy for other symptoms (OSE) was 42.6 (\pm 9.4) (32). Based on a minimal clinically important difference of 5.5 and population SD of 9.4, an effect size of approximately 0.59 was assumed. Additionally, based on previous research and outpatient clinic attendance experience, we expect dropout rate to be maximally 10% (13,24,33). Following these assumptions and in the setting of a superiority trial, 52 participants are needed in each group to detect a clinically meaningful difference in either PSE or OSE with 80% power and a significance level

of 0.05, while allowing for a 10% dropout rate.

It should be noted that the ASES score was not fully normally distributed in our aforementioned prospective study, implying that non-parametric tests might be needed to analyze the primary outcome. Following a general rule of thumb, sample size was thus increased by 15% to account for the loss of power these non-parametric tests would imply(34). Consequently, a total of 120 participants are needed (60 in each group) for the analysis of the primary outcome, with 80% power and a significance level of 0.05.

An additional sample size calculation was conducted for the secondary outcome of change in PCS score from baseline in the intervention group compared to the control group. Based on pooled data from the PCS development/validation studies and a French cohort of patients with RA, the population weighted mean (SD) PCS score is estimated at 20.3 (SD 12.3) (27,35,36). Thus, a clinically important difference in the PCS score, previously proposed as greater than 38% change (27,37), would correspond to a change in total PCS score of greater than 7.7/52. Aiming to exclude any (negative) effect of the intervention on change in the PCS score, we chose a non-inferiority design for this outcome. Given that the effect of the intervention on the PCS score is unknown, we chose the aforementioned minimal clinically important difference of 7.7 as the non-inferiority margin. In other words, non-inferiority will be confirmed if the upper bound of the 95% CI for the intervention's effect on PCS remains within a minimal clinically important margin(38). Following these assumptions and allowing for a 10% dropout rate, a total of 82 participants need to be included (41 in both the control and intervention groups) to demonstrate a non-inferior effect of the intervention on the PCS score with 80% power, a minimal clinically important margin and a two-sided significance level of 0.025. When 120 patients are included as per the primary outcome, and assuming a 10% drop-out rate, we should have 90.2% power to demonstrate non-inferiority for this secondary outcome.

Sample size calculations were conducted via R version 4.2.1, using the packages *pwr* and *epiR* (see Appendix B). In summary, a total of 120 patients will need to be included to assess both the primary outcome and the secondary outcome with at least 80% power, including 60 participants in both the control group and in the intervention group.

As described above, the intervention group will then again be randomized in a 1:1-ratio to assess the exploratory outcomes. The trial will thus not be powered for the exploratory analyses.

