Sample Size	
See page 27-28 for more detailed calculations.
 
N = 120.
 
For the primary outcome, sample size calculation was based on the minimal clinically important difference in the ASES-score, and on data from a recently published, large prospective study from our research group. Following these assumptions, 60 participants are needed in each group to detect a clinically meaningful change in ASES scores with 80% power and a significance level of 0.05, after adjusting for a 10% dropout rate and the possible need for non-parametric tests.
 
An additional sample size calculation was made for the secondary outcome of change in PCS score from baseline between the control and intervention group, using the proposed minimal clinically important difference in the PCS score, with pooled data from the PCS development/validation studies and a French cohort of patients with RA to estimate the population distribution. Aiming to exclude any (negative) effect of the intervention on change in the PCS score, we chose a non-inferiority design for this outcome. Given that the effect of the intervention on the PCS score is unknown, we chose the aforementioned minimal clinically important difference as the non-inferiority margin. Following these assumptions and allowing for a 10% dropout rate, a total of 82 participants need to be included (41 in both the control and intervention groups) to demonstrate a non-inferior effect of the intervention on the PCS score with 80%

	
power, a minimal clinically important margin and a two-sided significance level of 0.025. When 120 patients are included as per the primary outcome, and assuming a 10% drop-out rate, we should have 90.2% power to demonstrate non-inferiority for this secondary outcome.
 
In summary, a total of 120 patients will need to be included to assess both the primary outcome of self-efficacy and the secondary outcome of pain catastrophizing with at least 80% power, with 60 participants in both the control group and the intervention group.

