9.2 Analysis

Analyses will be carried out according to the intention-to-treat (ITT) principle, implying that participants will be analyzed based on the group they were originally assigned to.

In this study, the ITT population will consist specifically of all patients in the intervention group who effectively downloaded and installed the Sidekick application at the baseline visit, and all patients assigned to the control group. As stated above, participants in the intervention group will be re-randomized to intervention arm A or B, constituting two additional ITT populations that will only be analyzed exploratorily.

Per protocol (PP) analyses will be carried out as sensitivity analyses, including only those patients who completed the follow-up visit.

The variables described above in sections 4-6 will be extracted from the electronic medical patient file that is employed in all participating centers (KWS). Additionally, user behavior statistics and data actively logged by the patients in the app will be collected and provided for analysis in pseudonymized form by Sidekick Health. The primary and secondary outcome data of this study will be collected via questionnaires on the MyNexuzHealth app, or if not possible in pen-and-paper format at the outpatient clinic. All study-related information will be assembled and prepared for further analysis in an electronic CRF developed in REDCap. P-values <0.05 will be considered as statistically significant for all analyses. Missing data will be handled with multiple imputation by chained equations when data can be assumed to be missing at random. Descriptive statistics for baseline participant characteristics will be provided as means (\pm SD), medians (IQR) or proportions depending on data distribution.

Primary endpoint

The difference in mean change of total ASES (Arthritis Self-Efficacy Scale) score from baseline to week 16 \pm 2w in the intervention group when compared to the control group will be evaluated with an unpaired t-test or Wilcoxon rank sum test depending on distribution of the ASES-score. As a sensitivity analysis, we will additionally assess the difference between groups in week 16 scores using ANOVA adjusted for the baseline score. Furthermore, differences in the pain and other symptoms subscales of the ASES will be presented separately.

Secondary endpoints

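### The 80% power and N = 120 for the primary outcome are calculated for one ASES subscale, but the primary endpoint is change in total ASES

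*Combined protocol and SAP*

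**What the plan says.** Section 4.2 defines the primary endpoint as the between-group difference in mean change in total ASES, the sum of the pain (PSE) and other-symptoms (OSE) subscales, with range 11 to 110. Section 9.1 states the null hypothesis on the same variable: "no difference between the intervention and control groups in the change of the total ASES-score from baseline to week 16". Section 9.2 tests change in the total with a t-test or Wilcoxon test. For the subscales it says only that "differences in the pain and other symptoms subscales of the ASES will be presented separately".

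The inputs to the sample size are subscale figures. The minimal clinically important difference is described as "corresponding with a change of 5.5 on either the pain or other symptoms subscale". The SDs come from the group's 379-patient cohort: 8.9 for PSE and 9.4 for OSE. Section 9.1 continues: "Based on a minimal clinically important difference of 5.5 and population SD of 9.4, an effect size of approximately 0.59 was assumed". The resulting 52 per group are said to be enough "to detect a clinically meaningful difference in either PSE or OSE with 80% power".

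That number is then raised by 15% for possible non-parametric testing and becomes 120 for the primary outcome. The synopsis says "60 participants are needed in each group to detect a clinically meaningful change in ASES scores with 80% power", and section 9.1 closes by claiming 120 patients are enough "to assess both the primary outcome and the secondary outcome with at least 80% power". Appendix B labels the 5.5/9.4 calculation as the primary outcome and contains no calculation for the total score.

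**The concern.** The power statement describes a different variable from the one tested. A sum of two subscales has a larger SD than either alone unless they are clearly negatively correlated, and the difference to be detected on the sum depends on whether one or both subscales move. Neither quantity is given for the total, so the standardised effect of 0.59 has no stated link to the primary endpoint.

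There is a second gap. The endpoint is a change score, but 9.4 is a cross-sectional SD. The two are equal only if the correlation between baseline and week 16 is 0.5 and the SDs at both visits are the same.

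The validity of the primary test is not at stake. What is at stake is the stated justification for N and the reading of a null result: the plan does not say what difference in total ASES the trial was designed to detect.

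**Working it through.** **Reproducing the plan's figure.** The inputs are a difference of 5.5, SD 9.4, two-sided alpha 0.05, 80% power and a two-sample t-test (section 9.1 and Appendix B).

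- d = 5.5/9.4 = 0.585, which needs 46.83 per group, or 94 in total.
- Dropout: 94 × 1.10 = 103.4, or 52 per group.
- Non-parametric allowance: 103.4 × 1.15 = 118.9, hence 120.

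The stated N follows, but only from subscale inputs.

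**Basis for the total score.** 120 less 10% dropout is 108, or 54 per group. Figures in square brackets apply the plan's 15% allowance, 54/1.15 = 46.96 per group. Power is from the noncentral t distribution. The standardised difference detectable with 80% power is 0.544 [0.584].

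**Step 1: no correlation assumed.** The largest SD of change in total ASES that still gives 80% power is:

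- for a 5.5-point target, 5.5/0.544 = 10.1 [9.4];
- for an 11-point target (5.5 on each subscale), 11/0.544 = 20.2 [18.8].

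**Step 2: the plan's own convention, with the cross-sectional SD used as the SD of change.** The SD of the total is √(8.9² + 9.4² + 2·r·8.9·9.4), where r is the PSE–OSE correlation. The documents do not give r, so it is varied from 0 to 1.

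| r (assumed) | SD of total | Power, 5.5 on one subscale only | Power, 5.5 on both (11 points) | Detectable difference at 80% |
|---|---|---|---|---|
| 0 | 12.9 | 59% [53%] | 99% [98%] | 7.0 [7.6] |
| 0.3 | 14.8 | 48% [43%] | 97% [95%] | 8.0 [8.6] |
| 0.7 | 16.9 | 39% [35%] | 92% [88%] | 9.2 [9.9] |
| 1 | 18.3 | 34% [30%] | 87% [82%] | 10.0 [10.7] |

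**Step 3: change-score SD.** With equal SDs at both visits, SD of change = SD of total × √(2(1 − ρ)), where ρ is the baseline/week-16 correlation, also absent from the documents. Assume r from 0.3 to 0.9 and ρ from 0.3 to 0.8.

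- The SD of change runs from 14.8 × √0.4 = 9.3 to 17.8 × √1.4 = 21.1.
- Power for 5.5 points is 27% to 86% [24% to 81%].
- Power for 11 points is 77% to over 99% [about 70% to over 99%].
- The detectable difference is 5.1 to 11.5 points [5.5 to 12.3].

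**Step 4: correlation needed for 80% power.** Solving for ρ gives ρ = 1 − (maximum SD of change / SD of total)²/2.

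- For 5.5 points, 1 − (10.1/12.9)²/2 ≈ 0.70 at r = 0, rising to 1 − (10.1/18.3)²/2 ≈ 0.85 at r = 1 [0.74 to 0.87].
- For 11 points the worst case is r = 1: 1 − (20.2/18.3)²/2 ≈ 0.39 [0.47].

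**The case against.** The strongest reply is that the wording about either subscale may mean only that the same 5.5-point threshold applies to each, not that the gain is confined to one. If both gain 5.5, the standardised effect on the total is 11/18.3 = 0.60 to 11/12.9 = 0.85. That is never below the plan's 0.585, so on the plan's own use of cross-sectional SDs N = 120 is enough at every r from 0 to 1. This is correct, and it is why the finding cannot be stated as underpowering. But the plan does not state that assumption, and even an 11-point target falls short of 80% if ρ is low enough.

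Three further points have some force.

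- The lowest figures pair highly correlated subscales with a gain on only one of them. That is arithmetically possible but an awkward description of an intervention aimed at general self-efficacy. The figures are bounds, not forecasts.
- Any ρ above 0.5 makes the cross-sectional SD conservative. That is true, but a 5.5-point target would need about 0.70 to 0.85.
- A null result is read mainly from its confidence interval, and the version is dated late in the planned inclusion period. Both bear on urgency. Neither makes the stated 80% a statement about the primary endpoint, and the correction needs no change to conduct.

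The figure of 108 evaluable patients appears in Appendix B under the PCS calculation, but section 9.1 applies the same 10% dropout to the primary outcome.

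**Conclusion.** The concern holds. The 80% power and N = 120 stated for the primary outcome are correct for a test of one subscale and are not established for change in total ASES. Power for the primary endpoint could lie on either side of 80%. If 5.5 points are gained on one subscale only, it is below 80% over most of the range examined. If 5.5 are gained on both, it is above 80% over most of it. The result that needs no assumed correlation is the SD limit: at 54 per group, 80% power requires an SD of change in total ASES of at most 10.1 for a 5.5-point target or 20.2 for an 11-point target [9.4 and 18.8 with the non-parametric allowance]. All other ranges rest on assumed PSE–OSE and baseline/week-16 correlations and on equal SDs at both visits. The claim is wrong as written and should be corrected, but nothing here shows that the trial is too small or the test invalid.

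**What to change.** Keep N = 120, the endpoint, the test and alpha. In section 9.1, the synopsis and Appendix B:

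- State a target difference for total ASES. If the intention is 5.5 points on each subscale, or the same standardised effect of 0.59 on the total, say so and give the points on the total that this implies.
- In the script, replace 5.5/9.4 with that target divided by an SD of change in total ASES. Take the SD from the group's cohort if it supplies one. Otherwise use the total-score SD with a stated baseline/week-16 correlation and a range. Do not take it from this open-label trial's own outcome data.
- Restate the power or the detectable difference for 108 evaluable patients. Suggested text: *With 54 evaluable participants per group there is 80% power at two-sided 0.05 to detect a difference in change in total ASES of 0.54 SD (0.58 SD with the 15% non-parametric allowance), i.e. [x] points for an SD of change of [y] (source).* The sentence is informative only once x and y are filled in from a sourced SD.
- Remove the reference to either subscale from the power claim, and say whether a 5.5-point gain confined to one subscale is covered at 80%.

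The cost is a change of wording and script plus one input to source. The documents do not show that the cohort provides a 16-week SD of change, so a range may be needed. No extra patients are required and the analysis does not change. The stated power may become less favourable.
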